4.7.3 Compliance

The compliance of the study subjects will be supervised by the investigator. As the study substance will be dosed by a third person without any contact to the investigational team, the investigator will give the study substance (or placebo) to the study subject, who will swallow it under sight. The used cup and potential residues will be collected and stored by the investigator.

5 Study populations

5.1 Subject recruitment

Subjects will be recruited by addressing psychology and medical students of the University of Zurich by

public appointments. Subject eligibility will be confirmed through a brief telephone screening interview, which will be held by the principal investigator. Inclusion and exclusion criteria will be screened briefly during this interview. After a confirmation of eligibility, potential study subjects will have a personal meeting with the principal investigator and undergo medical examination and questionnaire testing.

5.2 Inclusion criteria

We will include healthy men between 20 and 40 years for PUK-GHB01 and healthy men between 20 and 30 years for PUK-GHB02. The subjects' capability to give informed consent will be approved by a psychologist involved in the study. An informed consent form must be signed by the subject before the start of the test.

5.3 Exclusion criteria

We will exclude female subjects, persons with intake of illegal psychotropic substances more than 5 times per substance or any psychiatric axis I disorder according to DSM-V or existence of a serious somatic or neurological disease. Screening will be performed using DIA-X. To exclude current illegal substance use drug urine test will be done at the beginning of each test session.

	Inclusion	Exclusion
General	
 - the subjects capability to give informed consent must be approved by a psychologist or resident physician involved in the study - an informed consent form must be signed by the subject before the start of the test 	
 - women - lifetime intake of illegal psychotropic substances on more than 5 occasions per substance - psychiatric axis I disorder according to DSM-IV - existence of a serious somatic or neurological disease -homosexual - smoking - medication
additional for PUK-GHB01	
 - men between 20 and 40 years - heterosexual 	
 - metal implants and big tattoos
additional for PUK-GHB02	
 - men between 20 and 30 years 	
 - sleep abnormalities (e.g. sleep apnea syndrome) (wakefulness after sleep onset > 20 %, apnea/hypopnea index > 5/hour of sleep, number of periodic leg movements > 5/hour of sleep) - metal implants and big tattoos

Table 3 Inclusion and exclusion criteria of subjects

6 Assessments of Effects

6.1 Outcome measures GHB01

Experiment	Method	Time (related to GHB application)
PUK-GHB01		
days	Cambridge neuropsychological automated test	t -40 min

1+2	battery (CANTAB) 1	
	GHB specific questionnaire (GSQ)	t -17, +38, +66, +106, +138 min, t+ 180 min
	Profile of Mood States (POMS)	t -13, +63, +141, +183 min
	Sexual arousal and desire questionnaire (SADI)	t -10, +51, +103, +160 min
	Visual Analog Scale (VAS)	t - 15 min, + 40, + 68, + 108, + 140, + 182 min
	Sexual Arousal Task	t + 41 min
	Movie for the Assessment of Social Cognition (MASC)	t +109 min
	Multifaceted empathy test (MET)	t +74 min
	Social Value Orientation (SVO)	t +90 min
	Charity Donation (CD)	t +69 min
	Reciprocity Task (RT)	t +163 min
	Social gaze test (SGT)	t +143 min
	Blood tests for endocrinology (BS-endo)	t-30 min, t0, t + 20 min, t + 35 min, t + 65 min, t +95 min, t + 124 min and t + 180 min
CANTAB 2	t >24 h	
days 3+4	Baseline-Scan	t - 30 min
	Post-Challenge Scan	t + 40-55 min
	SAT Task-related Scan	t + 60-80 min
	Post-Task Scan	t + 85-100 min

Table 4 Outcome measures GHB01: methods and time of testing

6.2 Outcome measures/Flow Chart GHB02

Prescreening		
Time point	Task	Time
	Telefoninterview	
	Zusenden des Fragebogenlinks und der Probandeninformation	
	Persönlichkeitsfragebogen	30-45 min
	Epworth Sleepiness Scale	
	Pittsburgh Sleep Quality Index	
	STAI-X ₂ (Trait)	
	BDI	
	SCL-90	
	MWT-B	
	Fragebogen ausgefüllt?	
	Probandenliste ergänzen	

Screening Night		

Time point	Task	Time
20:00	Empfang	15 min
	Einverständniserklärung	5 min
	Urine drug test	5 min
	Physical Examination	15 min
	Psychiatr. Interview (SKID-I Screening)	10 min
	Alcohol use identification test (AUDIT)	5 min
	Quednow Drug Interview	20 min
22:00	EEG/PSG installation	60 min
	Nail sample 1	
	Saliva_scre	
	Abend-Toilette	20 min
23:00	EEG/PSG connection (IMP)	
23:40	Subject in bed	
23:45	Karolinska Drowsiness Test	5 min
23:50	Waking EEG	10 min
00:00	SLEEP	420 min
08:00	CAR Saliva 1	
08:10	Karolinska Drowsiness Test	5 min
08:15	CAR Saliva 2	
08:15	Morning questionnaire (MQ)	5 min
08:20	Waking EEG	10 min
08:30	CAR Saliva 3	
08:30	EEG/PSG deconnection	10 min
	Morgen-Toilette (ohne Duschen)	10 min
08:45	CAR Saliva 4	
08:50	STAI-X1	5 min
08:55	EWL-60	15 min
09:10	Duschen etc.	
09:30	CAR Saliva 5	
	End of Session	

Adaptation Night 1		
Time point	Task	Time
21:30	Empfang	15 min
21:45	Blood sample 1 (Venflon; EDTA)	10 min
21:55	Drug/Alcohol test	5 min
22:00	EEG/PSG installation	60 min
	Saliva_adap1	
22:00	Light meal (optional)	
	Sweatpatch installation	
	Hair Sample 1	
	Abend-Toilette	
23:15	EEG/PSG connection (IMP)	20 min
23:35	Subject in bed	
23:45	Blood sample 2 (Venflon; EDTA)	2 min

	Karolinska Drowsiness Test	2 min
23:50	Waking EEG	10 min
0:00	SLEEP	420 min
08:00	Blood sample 3 (Venflon; EDTA)	5 min
08:10	Karolinska Drowsiness Test	5 min
08:15	Morning questionnaire (MQ)	5 min
08:20	Waking EEG	10 min
08:30	EEG/PSG deconnection	10 min
	Morgen-Toilette/Urine sample 1	10 min
8:40	Random Number Generation Task (RNG)	10 min
8:50	Psychomotor Vigilance Task incl. SSS	10 min
9:00	STAI-X1	5 min
9:05	EWL-60	15 min
9:20	Duschen etc.	
	End of Session	

Experimental Night 1		
Time point	Task	Time
19:30	Empfang	15 min
20:00	Blood sample 1 (Venflon; 2 EDTA; Protein, Kalium-Fluorid, Heparin-Plasma, 2 PAX)	15 min
20:40	Drug/Alcohol test	5 min
20:45	EEG/PSG installation	60 min
	Saliva_exp1	
	Light meal (optional)	
	Sweatpatch installation	
21:45	STAI-X1, PANAS, EWL-60, EQ, VAMS	20 min
22:05	Paired Word List Task 1	40 min
22:45	Walker 1	10 min
	Abend-Toilette	
23:10	EEG/PSG connection	20 min
	Subject in bed	
23:30	*** GHB or Placebo ***	5 min
23:47	Karolinska Drowsiness Test	2 min
23:50	Waking EEG	10 min
23:55	Blood sample 2 (Venflon; 2 EDTA, Protein, Kalium-Fluorid, Heparin-Plasma, 2 PAX)	5 min
00:00	SLEEP	420 min
08:00	CAR Saliva 1	
	Blood sample 3 (Venflon; 2 EDTA, Protein, Kalium-Fluorid, Heparin-Plasma, 2 PAX)	10 min
08:10	Karolinska Drowsiness Test	5 min
08:15	CAR Saliva 2	
	Morning questionnaire (MQ)	5 min
08:20	Waking EEG	10 min
08:30	CAR Saliva 3	
	EEG/PSG deconnection	10 min

08:40	Morgen-Toilette/Urine sample 2	10 min
08:45	CAR Saliva 4	
08:50	Paired Word List Task 2	40 min
09:30	CAR Saliva 5	
09:35	Walker 2	10 min
09:45	IOWA Gambling Task (IGT)	20 min
10:05	Random Number Generation Task (RNG)	10 min
10:15	Psychomotor Vigilance Task incl. SSS	10 min
10:25	Delay discounting task	5 min
10:30	STAI-X1, PANAS, EWL-60, EQ, VAMS	20 min
10:50	Duschen etc.	
	End of Session	

Post Acute Measurement 1		
Time point	Task	Time
12:00 (t12h)	PANAS, EWL-60, VAMS	
16:00 (t16h)	PANAS, EWL-60, VAMS	
19:45	Empfang	
20:00 (t24h)	PANAS, EWL-60, VAMS	
	Blood sample 4 (Venflon; 2 EDTA, Protein, Kalium-Fluorid, Heparin-Plasma, 2 PAX)	
	Nail sample 2	

Adaptation Night 2		
Time point	Task	Time
21:30	Empfang	15 min
21:45	Blood sample 1 (Venflon; EDTA)	10 min
21:55	Drug/Alcohol test	5 min
22:00	EEG/PSG installation	60 min
	Saliva_adap2	
22:00	Light meal (optional)	
	Sweatpatch installation	
	Hair Sample 1	
	Abend-Toilette	
23:15	EEG/PSG connection (IMP)	20 min
23:35	Subject in bed	
23:45	Blood sample 2 (Venflon; EDTA)	2 min
	Karolinska Drowsiness Test	2 min
23:50	Waking EEG	10 min
0:00	SLEEP	420 min
08:00	Blood sample 3 (Venflon; EDTA)	5 min
08:10	Karolinska Drowsiness Test	5 min
08:15	Morning questionnaire (MQ)	5 min
08:20	Waking EEG	10 min
08:30	EEG/PSG deconnection	10 min

	Morgen-Toilette/Urine sample 1	10 min
8:40	Random Number Generation Task (RNG)	10 min
8:50	Psychomotor Vigilance Task incl. SSS	10 min
9:00	STAI-X1	5 min
9:05	EWL-60	15 min
9:20	Duschen etc.	
	End of Session	

Experimental Night 2		
Time point	Task	Time
19:30	Empfang	15 min
20:00	Blood sample 1 (Venflon; 2 EDTA, Protein, Kalium-Fluorid, Heparin-Plasma, 2 PAX)	15 min
20:40	Drug/Alcohol test	5 min
20:45	EEG/PSG installation	60 min
	Saliva_exp2	
	Light meal (optional)	
	Sweatpatch installation	
21:45	STAI-X1, PANAS, EWL-60, EQ, VAMS	20 min
22:05	Paired Word List Task 1	40 min
22:45	Walker 1	10 min
	Abend-Toilette	
23:10	EEG/PSG connection	20 min
	Subject in bed	
23:30	*** GHB or Placebo ***	5 min
23:47	Karolinska Drowsiness Test	2 min
23:50	Waking EEG	10 min
23:55	Blood sample 2 (Venflon; 2 EDTA, Protein, Kalium-Fluorid, Heparin-Plasma, 2 PAX)	5 min
00:00	SLEEP	420 min
08:00	CAR Saliva 1	
	Blood sample 3 (Venflon; 2 EDTA, Protein, Kalium-Fluorid, Heparin-Plasma, 2 PAX)	10 min
08:10	Karolinska Drowsiness Test	5 min
08:15	CAR Saliva 2	
	Morning questionnaire (MQ)	5 min
08:20	Waking EEG	10 min
08:30	CAR Saliva 3	
	EEG/PSG deconnection	10 min
08:40	Urine sample 2	10 min
08:45	CAR Saliva 4	
08:50	Paired Word List Task 2	40 min
09:30	CAR Saliva 5	
09:35	Walker 2	10 min
09:45	IOWA Gambling Task (IGT)	20 min
10:05	Random Number Generation Task (RNG)	10 min
10:15	Psychomotor Vigilance Task incl. SSS	10 min

10:25	Delay discounting task	5 min
10:30	STAI-X1, PANAS, EWL-60, EQ, VAMS	20 min
10:50	Duschen etc.	
	End of Session	

Post Acute Measurement 2		
Time point	Task	Time
12:00 (t12h)	PANAS, EWL-60, VAMS	
16:00 (t16h)	PANAS, EWL-60, VAMS	
19:45	Empfang	
20:00 (t24h)	PANAS, EWL-60, VAMS	
	Blood sample 4 (Venflon; 2 EDTA, Protein, Kalium-Fluorid, Heparin-Plasma, 2 PAX)	
	Nail sample 2	

Time point	Sample	Time
Screening night	Nail sample 1	
Adapt night 1	Hair sample 1	
Post akut 1	Nail sample 2	
Adapt night 2	Hair sample 2	
Post akut 2	Nail sample 3	
2 days post EN 2	Hair sample 3	
2 weeks post EN 2	Nail sample 4 (at home)	
3 weeks post EN 2	Nail sample 5 (at home)	
4 weeks post EN 2	Nail sample 6 (at home)	
5 weeks post EN 2	Hair sample 4	
	Nail sample 7	
6 weeks post EN 2	Nail sample 8 (at home)	
7 weeks post	Nail sample 9 (at home)	

EN 2		
8 weeks post EN 2	Nail sample 10 (at home)	
9 weeks post EN 2	Nail sample 11 (at home)	
10 weeks post EN 2	Nail sample 12 (at home)	
11 weeks post EN 2	Nail sample 13 (at home)	
12 weeks post EN 2	Nail sample 14 (at home)	
13 weeks post EN 2	Nail sample 15 (at home)	
14 weeks post EN 2	Nail sample 16 (at home)	

Experimental night 3		
Zeit (geplant)	Task	Time
21:15	Empfang	
21:30	Drug/Alcohol test	
21:55	Blood sugar measurement	
22:00	Light meal (optional)	
22:15	MR-Fragebogen, VAS, PANAS, VAMS, EQ	
22:20	EEG/PSG installation	
	Sweatpatch 5	
23:00	MRI Baseline	
	Anatomisches MRI	
	MRS	
	Resting Sate fMRI	
23:30	***GHB or Placebo***	
00:00	Blood Sample 1 (Butterfly; 2 EDTA)	
00:05	MRI Session 1	
	Anatomisches MRI	
	MRS NAcc, ACC, Amygdala	
	Resting Sate fMRI	
01:40	Blood Sample 2 (Butterfly; 2 EDTA)	
01:45	VAS, PANAS, VAMS	
	Abend Toilette	
	EEG/PSG connection	
01:50	Karolinska Drowsiness Test	

02:00	Waking EEG	
	Sleep	
08:00	Karolinska Drowsiness Test	
08:05	Morning questionnaire	
08:10	Waking EEG	
08:20	VAS, PANAS, VAMS,	
	Hair sample 2	
	EEG disconnection	
	Morgen-Toilette	
	EEG connection	
08:30	MRI Session 2	
	Anatomisches MRI	
	MRS NAcc, ACC, Amygdala	
	Resting State fMRI	
	EEG disconnection	
10:10		
	End of session	

Experimental night 4		
Zeit (geplant)	Task	Time
21:15	Empfang	
21:30	Drug/Alcohol test	
21:55	Blood sugar measurement	
22:00	Light meal (optional)	
22:15	MR-Fragebogen, VAS, PANAS, VAMS, EQ	
22:20	EEG/PSG installation	
	Sweatpatch 6	
23:00	MRI Baseline	
	Anatomisches MRI	
	MRS	
	Resting State fMRI	
23:30	***GHB or Placebo***	
00:00	Blood Sample 1 (Butterfly; 2 EDTA)	
00:05	MRI Session 1	
	Anatomisches MRI	
	MRS NAcc, ACC, Amygdala	
	Resting State fMRI	
01:40	Blood Sample 2 (Butterfly; 2 EDTA)	
01:45	VAS, PANAS, VAMS	
	Abend Toilette	
	EEG/PSG connection	
01:50	Karolinska Drowsiness Test	
02:00	Waking EEG	
	Sleep	

	Karolinska Drowsiness Test	
08:00		
	Morning questionnaire	
08:05		
08:10	Waking EEG	
08:20	VAS, PANAS, VAMS,	
	Hair sample 2	
	EEG disconnection	
	Morgen-Toilette	
	EEG connection	
08:30	MRI Session 2	
	Anatomisches MRI	
	MRS NAcc, ACC, Amygdala	
	Resting State fMRI	
	EEG disconnection	
10:10		
	End of session	

7 Safety

7.1 Safety measures

Experiment	Method	Time (related to GHB application)
PUK-GHB01 days1+2	Blood pressure/pulse (BP/P)	t -40, 0, +20, +40, +120 min
PUK-GHB02	Supervision, EEG-Measures	see Flow Chart 6.2

Table 5 Safety measures: methods and time of testing

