4.2 Design of the Experiments PUK-GHB01 and PUK-GHB02

4.2.1 PUK-GHB01: social cognition and hormones

Thirty-two male healthy subjects will be assessed with questionnaires (GHB Specific Questionnaire [GSQ], Sexual Arousal and Desire Questionnaire [SADI], Profile of Mood States [POMS], Visual Analog Scale [VAS]), tests of social cognition (Sexual Arousal Task [SAT], Multifaceted Empathy Test [MET], Social Gaze Test [SGT], Movie for the Assessment of Social Cognition [MASC]), neuropsychology (Cambridge Neuropsychological Automated Test Battery [CANTAB], Flanker Task, Verbal Memory Test [VLMT]), neuroeconomic tests (Reciprocity Task [RT], Social Value Orientation [SVO], Charity Donation [CD]), electroencephalography (EEG), functional magnet resonance imaging (fMRI) and neuroendocrine blood tests (oxytocin, 3,5-THP, THDOC, ACTH, prolaktin, testosterone, cortisol, progesterone, N-Arachidonoylethanolamin, 2-Arachidonoylglycerol, Palmitoylethanolamid, Arachidonic acid, Linoleboylethanolamid, Oleoylethanolaid, Stearoylethanolamid, prostaglandin E2 and GHB) after application of GHB (days 1+2 20 or 35 mg/kg p.o., days 3+4 35 mg/kg p.o. vs. placebo – cross over design). The neuropsychological and neuroeconomic test as well as the tests of social cognition have already been implemented in trials of the Experimental and Clinical Pharmacopsychology research group of the Psychiatric University Hospital Zurich. The neurocognitive test will be performed on a study computer of the experimental and clinical pharmacopsychology research group of the Psychiatric University Hospital Zurich. The fMRI experiments will be performed at the MR Center of the University Hospital of Psychiatry Zurich. The assessment will follow the Good Clinical Practice (GCP) guidelines. Both neurocognitive and neuroendocrine tests will be performed paralleled, under two different conditions (20 or 35 mg/kg GHB p.o. vs. placebo; t₀= GHB application) on two days spaced at least 1 week apart. Neurocognitive testing will be performed during the peak of subjective GHB effects (t+ 30 until t + 90). Blood tests for neuroendocrinologic measures will be taken six times (t-30 min, t₀, t + 20 min, t + 35 min, t + 65 min, t +95 min, t + 124 min and t + 180 min). A total amount of blood of 150 ml will be taken during each experiment. The complete assessment will last about five hours. The two fMRI sessions will start at least one week after the two first experimental days, and succeed with at least one week in between. Each session takes a time of 2.5 hours. Furthermore, one pre- and one post-test session will be performed for medical check-up.

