4.3.3 Neuroeconomical testing

We will perform the Social Value Orientation (SVO), Charity Donation (CD) and Reciprocity Task (RT) to assess changes in neuroeconomical reactions under the influence of the drug.

The Reciprocity Task is a monetary distribution task, which is used to investigate the social behavior between two participants. Out of time and infrastructural reason, it is not possible to conduct an interaction between various subjects. That's why a cover story had to be used to create a reliable social interaction condition. So, the subjects are told that they were interacting with other study participants, whereas they interacted just with virtual participants.

The task consists of five interactions with five virtual participants. In each interaction the subject is asked to distribute a value between 0 - 8.- CHF between himself and the opposite (virtual) participant. This task allows to a certain extent to measure the degree of altruism in a monetary distribution situation.

In the Charity Donation Task, participants are given the possibility to donate a value between 0-40.- CHF of their own monetary participant compensation to one of ten listed charity organizations. After that the subjects are asked to rate how pleased they felt about their donation. The participants are further informed that only one of both donations of the two main testing sessions would randomly be chosen to be paid out. The Social Value Orientation (SVO) is another monetary distribution test, which is used to characterize the social behavior of a subject. It allows assigning the subjects to either an altruistic, prosocial, individualistic or competitive category.

We use a SVO version composed of 15 different decision scales. The subjects are instructed to choose for each scale the preferred monetary distribution. They are further told that their decision would directly affect their one final monetary participant compensation (You receive) and the one of the next participant of the study (other receives).

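### On PUK-GHB01 days 1+2, no blood pressure or pulse reading is scheduled between t+40 and t+120 or after t+120; readings at t+65, t+95, t+180 and discharge would narrow both gaps at low cost

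*Combined protocol and SAP*

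**What the plan says.** Section 7.1, Table 5, gives the blood pressure and pulse times for PUK-GHB01 days 1+2 as "t -40, 0, +20, +40, +120 min". This is the only blood pressure schedule in the document.

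The rest of the session is set out in sections 4.2.1 and 6.1:

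- **Session length (4.2.1):** "The complete assessment will last about five hours". The text does not say where those five hours begin relative to dosing.
- **Subjective peak (4.2.1):** "Neurocognitive testing will be performed during the peak of subjective GHB effects (t+ 30 until t + 90").
- **Blood draws (6.1, Table 4):** "t-30 min, t0, t + 20 min, t + 35 min", then "t + 65 min, t +95 min, t + 124 min and t + 180 min". Section 4.2.1 lists the same eight times but speaks of six draws.
- **Late assessments (6.1, Table 4):** the GHB questionnaire (GSQ) at "t -17, +38, +66, +106, +138 min, t+ 180 min" and the mood profile (POMS) at "t -13, +63, +141, +183 min". The POMS at t+183 is the last timed item of the day.

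On supervision, sections 4.2.1 and 7.2 put a doctor in charge of the sessions. Section 7.2 asks for particular attention to disinhibition, dizziness, nausea, drowsiness and impaired breathing. Section 12.4 includes vital signs in the safety module of the case report form, without times.

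**The concern.** The readings cluster in the first 40 min after dosing and then thin out. The stretch with no scheduled reading takes in most of the period in which the protocol expects the strongest subjective effects, and the remainder of the session after t+120 has none.

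The drug is sedating. Section 2.4 says that 30-50 mg/kg brings on sleep and general anaesthesia, and half of the men receive 35 mg/kg on these days. Section 2.3 lists raised arterial pressure among the common side effects, without onset or duration. A supervising doctor would notice the reactions named in section 7.2, but a symptomless change in blood pressure needs a cuff. A change that starts after t+40 and resolves before t+120, or that starts after t+120, would not be recorded by the schedule.

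What is at stake is the completeness of safety monitoring in healthy volunteers. No endpoint or planned analysis uses these readings.

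**Working it through.** The plan states no figure to reproduce here; the check is interval arithmetic on the times in Tables 4 and 5. All times are minutes from dosing.

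**Current gaps.** Differences between successive readings at -40, 0, 20, 40, 120:

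- 0 - (-40) = 40; 20 - 0 = 20; 40 - 20 = 20; 120 - 40 = 80.
- Part of the 80-min gap inside the subjective-effect window [30, 90]: 90 - 40 = 50 of 60 min.
- From the last reading to the last timed item: 183 - 120 = 63 min.

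**Which draws could carry a reading.** Listed draws after t+40 are at 65, 95, 124 and 180. The draw at 124 falls 4 min after the existing reading at 120 and adds little. Of the possible sets of three, {65, 95, 180} is the only one that both brings the longest interval within t+40 to t+120 down to 30 min and extends readings to t+180:

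| Added readings | Longest interval within t+40 to t+120 | Last reading |
|---|---|---|
| 65, 95, 124 | 30 | 124 |
| 65, 95, 180 | 30 | 180 |
| 65, 124, 180 | 55 | 180 |
| 95, 124, 180 | 55 | 180 |

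**Gaps with 65, 95 and 180 added.**

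- 65 - 40 = 25; 95 - 65 = 30; 120 - 95 = 25; 180 - 120 = 60.
- Unread stretches inside [30, 90]: 10 and 50 min now; 10, 25 and 25 min afterwards.
- Post-dose readings at fixed times (after t0): 3 now, 6 afterwards.

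**Unread time at the end of the session.** This depends on where the five hours (300 min) begin, which is an assumption:

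| Assumed start | End of session | Tail after t+120 | Tail after t+180 |
|---|---|---|---|
| t-40 (earliest timed item) | -40 + 300 = 260 | 140 | 80 |
| dosing (t0) | 0 + 300 = 300 | 180 | 120 |
| before t-40, ending no earlier than the last POMS | 183 | 63 | 3 |

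That no reading is scheduled after t+120 is independent of the assumption; the length of the tail is not.

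**Number of readings.** 32 men x 2 sessions x 3 = 192. At an assumed 2 min each, 384 min = 6.4 h (3.2 to 9.6 h at 1 to 3 min). A discharge reading adds 32 x 2 = 64, giving 256 readings and 512 min = 8.5 h (4.3 to 12.8 h).

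**The case against.** The strongest reply is that this comes close to a preference. The documents contain no time course for blood pressure or pulse, the t+30 to t+90 window describes subjective effects, and the only support for a pressure change is one entry in a list of side effects in treated patients. That stands, and it limits the weight of the point.

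The safeguards are also more than nominal. Besides the supervision in section 7.2, which covers breathing, section 4.5.1 has the principal investigator drawing the blood, so there is direct contact at the proposed times. Unscheduled readings are not excluded and can be recorded. Section 4.2.1 provides for stopping at once and for a post-test medical check-up, and section 7.2 for emergency transfer. A reader might infer from Table 5 that volunteers go unmonitored for 80 min; these provisions show otherwise. What they do not do is require a cuff reading.

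It can further be said that no link between blood pressure readings and blood draws is stated. That is correct: the times coincide at t0 and t+20, while the other three (-40, +40, +120) fall near draws at -30, +35 and +124 without matching them. Since six or eight draws may be taken, a proposed reading could also lose its accompanying draw.

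Finally, days 1+2 are the only sessions with any blood pressure schedule, and half of the men receive just 20 mg/kg then. This argues for low priority but does not remove the gaps.

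**Conclusion.** The point holds as a minor one on safety monitoring. Two facts are firm: an 80-min interval without a scheduled reading, covering 50 of the 60 min of the stated subjective peak, and no scheduled reading after t+120 although assessments continue to t+183.

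A reader might go further and infer that the schedule misses a haemodynamic peak. The documents do not support that, because they give no course of blood pressure or pulse after dosing and so do not show whether any change occurs in the gaps. Nor would three added readings close the gaps: 60 min would remain between t+120 and t+180, and the session may run on for 3 to 120 min after t+180, depending on where the five hours start. For that reason t+180 alone cannot be taken to document recovery.

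**What to change.** In Table 5, keep the five readings and add blood pressure and pulse at t+65, t+95 and t+180, on the arm without the catheter, plus one reading before discharge. If a listed draw is not taken, keep the reading at its clock time. No action threshold is proposed here.

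The cost is the 256 readings worked out above, with no extra staff and no invasive procedure. If the cuff does not fit within the draw, nearby items may slip by about 2 min:

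- **t+65** sits between POMS at +63 and GSQ at +66. A delay could carry to the visual analogue scale (VAS) at +68 and Charity Donation at +69, and to the empathy test at +74 unless Charity Donation takes 3 min or less of its 5-min slot (74 - 69 = 5; 5 - 2 = 3). Its duration is not given.
- **t+95** may overlap Social Value Orientation, which starts at +90 with no stated duration (section 4.3.3: "We use a SVO version composed of 15 different decision scales"). The listed draw may already do so.
- **t+180** coincides with GSQ and comes just before VAS at +182 and POMS at +183.

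These tests and questionnaires are among the primary outcome measures in section 4.1, so the slippage deserves attention. The planned times are the same under GHB and placebo, but actual delays may differ in sedated subjects. The plan already accepts one slot as tight: the reading at +40 shares its time with VAS and precedes the Sexual Arousal Task at +41. The discharge reading delays no timed item.

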2.3 Side effects

Typical side effects (10-20% of the treated patients) of GHB are dizziness, nausea and headaches. Common side effects ($\geq 1/100$ to $< 1/10$) are anorexia, abnormal dreaming, drowsiness, disorientation, somnambulism, depression, sleep disturbances, cataplexy, fear, insomnia, nervousness, somnolence, tremor, imbalance, falls, attention deficits, hypesthesia, paresthesia, sedation, blurred vision, arterial hypertonia, dyspnea, snoring, emesis, gastric pain, diarrhea, sweating, muscle cramps, arthralgia, enuresis, asthenia, sleepiness, peripheral edema. Occasional side effects ($\geq 1/1000$ to $< 1/100$) are weight loss, psychosis, paranoia, abnormal thinking, hallucinations, agitation, suicide attempt, sleep disorder, myoklonus, amnesia, restless leg syndrome, eczema (Compendium, 2010).

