2.4 Toxicity

The toxic effects of GHB are dose-dependent: low doses (10 mg/kg) induce euphoria, increased libido, and disinhibition, while doses of 30-50 mg/kg lead to sleep and general anesthesia (Wong et al., 2004). The median lethal dose (LD_{50}) of GHB in rats is 1.7 g/kg (Snead, 2002). In humans, massive overdoses and the combination of GHB with CNS depressants such as alcohol are associated with serious coma necessitating

intubation and intensive care, the number of reported fatal cases associated with the drug appears very limited. Post-marketing surveillance indicates GHB has an acceptable safety profile for controlled clinical application (Wedin et al., 2006).

3 Aims of the project

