11.1 Risk-benefit analysis

We aim to perform a pharmacological challenge study with GHB under two circumscribed conditions (wake and sleep) with two single expositions to the substance compared to placebo for each subject in the first experiment and two single expositions in the second experiment. GHB is internationally approved for the

27/32

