treatment of narcolepsy and was shown to have a favorable safety profile both for therapeutic and experimental use (Kantrowitz et al., 2009). However, concern has been raised regarding toxicity and possible dependency from GHB and the possibility of its misuse or abuse (Nicholson and Balster, 2001). The risk of acute toxicity using the herein proposed doses is extremely low, as multicenter studies and post marketing surveillance for GHB (Xyrem) suggested a very low incidence of unexpected side effects even in long term use (Wang et al., 2009). Residual toxicity of GHB is very small as endogenous and exogenous GHB is rapidly and completely converted into CO₂ and H₂O through the tricarboxylic acid cycle (Krebs cycle) (Maitre, 1997). Regarding the often cited concern about the potential addictive effect of GHB, animal studies showed a relatively low reinforcing effect compared to barbiturates and benzodiazepines. GHB and its precursors 1,4-butanediol (BDL) and gamma-butyrolactone (GBL) were not able to substitute for pentobarbital, methohexital, midazolam, diazepam or flumazenil in rhesus monkeys. Self-administration was lower than with these substances and the total maintained self-administration was marginally above saline levels (McMahon et al., 2003). In humans, a clear differentiation has to be done between illicit uncontrolled and medically supervised use of the substance. Cases of physical dependence have been reported in recreational illicit GHB users, but exact statistical analysis remains difficult as the estimated number of unreported non-dependent users is not known (Miotto et al., 2001, Degenhardt et al., 2002). Compared to this, reported rates of substance dependency as defined by DSM-IV criteria and physical dependency respectively, after the use of therapeutically applied GHB are one case for every 6500 patients treated and one case for every 3300 patients treated, or approximately 0.015% and 0.031% (Wang et al., 2009). These data apply to controlled daily use over periods up to 30 years. Thus, the cumulative post marketing and clinical experience indicates a very low risk of abuse/misuse of therapeutically applied GHB. Given that this study implies only a maximum of four exposures to the drug in doses, which are lower or equivalent to therapeutic doses, and that the expected results are important for the understanding of the complex relationships between hormonal, cerebral, cognitive and behavioral functions in humans, the risk-benefit analysis clearly suggests a benefit for conducting both trials.

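### Table 5 schedules blood pressure and pulse only on PUK-GHB01 days 1+2, so 72 of 104 planned GHB doses have no scheduled blood pressure reading; the firmest gap is the 32 doses on fMRI days 3+4

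*Combined protocol and SAP*

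**What the plan says.** Table 5 in section 7.1 has two rows. The row for "PUK-GHB01 days1+2" sets blood pressure and pulse at "t -40, 0, +20, +40, +120 min". The row for PUK-GHB02 gives "Supervision, EEG-Measures" and refers to the flow chart in 6.2. PUK-GHB01 days 3+4 have no row, and Table 4 (section 6.1) lists only four scans for those days.

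The 6.2 flow chart itemises saliva, sweat patches, blood tubes and blood sugar, but shows no blood pressure or pulse on any dosing night. Section 4.2.2 includes pulse oximetry in the polysomnography. On nights 1+2 the EEG/PSG is connected at 23:10, before the 23:30 dose. On nights 3+4 it is installed at 22:20, but a connection is listed only after 01:45.

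On risk, section 2.4 states that "doses of 30-50 mg/kg lead to sleep and general anesthesia" and also that "GHB has an acceptable safety profile for controlled clinical application". Section 2.3 places "blurred vision, arterial hypertonia, dyspnea" among the common side effects. Section 11.1 concludes: "The risk of acute toxicity using the herein proposed doses is extremely low".

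**The concern.** On days 1+2 the sponsor scheduled five readings per session at 20 or 35 mg/kg. At the same or a higher dose in the other sessions, none is scheduled and no reason is given. Followed as written, the schedule leaves blood pressure after most doses to the judgement of whoever is present.

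Two things are at stake. First, raised blood pressure is listed as a common effect, and of the measures listed only a cuff reading would show it. Second, section 7.2 singles out respiratory impairment for attention, yet no listed measure on fMRI days 3+4 would track saturation or pulse while the man is in the scanner after dosing.

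**Working it through.** **Inputs.** Section 4.7.2 gives 32 men in PUK-GHB01: 16 at 20 mg/kg and 16 at 35 mg/kg on days 1+2, then all 32 at 35 mg/kg once across the MR sessions. It gives 20 men in PUK-GHB02 with 50 mg/kg on two occasions. Section 11.1 agrees on exposures per man: "two single expositions to the substance compared to placebo for each subject in the first experiment and two single expositions in the second experiment".

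**Total.** 32 × 2 + 20 × 2 = 104 planned GHB doses. The plan states no dose total or coverage figure to reproduce. One check is the drug quantity in 4.6.1. For experiment 2, 40 doses × 50 mg/kg × 70 kg = 140,000 mg, as stated. For experiment 1, 70 × (16 × 20 + 16 × 35 + 32 × 35) = 140,000 mg against a stated 116,900 mg. The count of 64 doses there therefore rests on 4.7.2 and 11.1, not on the drug quantity.

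**Coverage by block.**

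| Sessions | GHB doses | BP/pulse scheduled | Oximetry listed in first 2 h |
|---|---|---|---|
| PUK-GHB01 days 1+2 | 32 (16 at 20, 16 at 35 mg/kg) | yes | no |
| PUK-GHB01 days 3+4 | 32 (35 mg/kg) | no | no |
| PUK-GHB02 nights 1+2 | 20 (50 mg/kg) | no | yes, from t−20 min |
| PUK-GHB02 nights 3+4 | 20 (50 mg/kg) | no | unclear |

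- No scheduled blood pressure: 32 + 20 + 20 = 72; 72/104 = 69.2%.
- Neither blood pressure/pulse nor oximetry listed in the first two hours, firm: 32/104 = 30.8% (days 3+4).
- The same, if oximetry on nights 3+4 starts only at the listed connection: 32 + 20 = 52; 52/104 = 50.0%. From 23:30 to 01:45 is 135 min.

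**First exposures on days 3+4.** These sessions follow days 1+2 by at least a week (4.2.1). The 16 men who had 20 mg/kg receive 35 mg/kg for the first time in the study there, 35/20 = 1.75 times their previous dose. The gap is therefore not confined to repeat doses.

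**Room for readings.**
- Days 3+4: the baseline scan starts at t−30 and takes 10 + 5 + 5 = 20 min (4.3.6), ending at t−10. Later scans run t+40 to 55, t+60 to 80 and t+85 to 100. Times before dosing, at t+20, at t+30 to t+35 and from t+100 are free.
- A 150-minute session (4.2.1) containing t−30 to t+100 (130 min) has 20 min of slack, so it ends between t+100 and t+120. A t+120 check adds 0 to 20 min.
- PUK-GHB02 nights 1+2: the 5-minute dosing entry ends at 23:35 and the next item is at 23:47 (t+17). The 08:00 contact is t+510.
- PUK-GHB02 nights 3+4: the blood draws at 00:00 and 01:40 are t+30 and t+130. The post-dose MRI starts at 00:05 (t+35).

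**The case against.** The best case for the plan has four parts.

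**Other safeguards exist.** A physician oversees each series and emergency transfer is assured (7.2). A doctor monitors PUK-GHB01, which also has medical check-ups before and after (4.2.1). PUK-GHB02 is monitored too (4.2.2). The CRF safety module records vital signs without limiting them to days 1+2 (12.4). This stands, and a reader who inferred that nothing would be measured in the other sessions would go beyond the text. None of these provisions, however, sets a time or a session.

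**The 69% overstates the gap.** For 20 of the 72 doses, oximetry is running before the dose and would normally show pulse as well. This stands: on those nights mainly blood pressure is missing. A reader might also take the 50% figure as established. It is not. The late connection on nights 3+4 follows the evening toilet break, the next morning's chart has a disconnection and reconnection around the toilet, and EEG is planned with the scans (4.3.6, 4.3.7). It may be a reconnection. In-scanner oximetry is nevertheless not listed.

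**The doses are ordinary.** Section 2.2.2 calls 50 mg/kg common in narcolepsy treatment. Section 2.2 gives about 65 to 130 mg/kg per night in two equal doses, so about 32.5 to 65 mg/kg per dose, and sleep is the intended effect in PUK-GHB02. This stands. It is also tempting to read the schedule as monitoring that shrinks as dose rises. But 35 mg/kg is covered on days 1+2 and uncovered only on the fMRI days, so setting and dose cannot be separated.

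**Cuff readings miss the peak.** Section 4.2.1 puts peak subjective effects at t+30 to t+90 for the awake sessions. Readings outside sleep and scans can reach only the start of that window on days 3+4 and nights 3+4, and none of it on nights 1+2. This stands, and is why oximetry belongs in the fix.

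**Conclusion.** The gap in the schedule is real and worth closing, but modest. Blood pressure is not scheduled for 72 of 104 planned GHB doses (69%). The firm core is PUK-GHB01 days 3+4: 32 doses (31%) with neither blood pressure/pulse nor oximetry listed, 16 of them a man's first 35 mg/kg dose in the study. PUK-GHB02 nights 1+2 lack mainly blood pressure. Nights 3+4 add 20 doses to the core only if oximetry starts at the listed connection.

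The counts assume that all men complete and all have their MR sessions; 4.5.1 speaks of at least two sessions in experiment I, so fewer MR doses are possible. They also assume that Figure 1 and Chart 1, which I could not see, add no vital-sign times; their captions describe flow and session order.

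A reader might infer that harm is expected. The documents do not support that. The frequency for raised blood pressure (at least 1% and under 10%) concerns treated patients, not single doses, and yields no expected number of events here.

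**What to change.** Extend Table 5 to every dosing session, identically for GHB and placebo:

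- **PUK-GHB01 days 3+4:** blood pressure and pulse before dosing, at t+20, just before the post-challenge scan (about t+30 to t+35), after the post-task scan (about t+100) and at t+120.
- **PUK-GHB02 nights 1+2:** blood pressure before dosing, at about t+15 and at 08:00.
- **PUK-GHB02 nights 3+4:** blood pressure before dosing, at the 00:00 and 01:40 blood draws and in the morning.
- **Oximetry:** name polysomnography pulse oximetry as a PUK-GHB02 safety measure. Run it from before dosing on nights 1+2 and, outside the scanner, on nights 3+4. State in the flow chart when it starts.
- **Post-dose scans:** use an MR-compatible pulse sensor if one is already available.

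The change touches 32 × 2 + 20 × 4 = 144 sessions, counting GHB and placebo. It needs an amendment to Table 5 and the flow charts, a few minutes per session at existing contacts, and up to 20 minutes' longer stay on fMRI days. No new visits or staff are needed, and no reading falls within sleep or a scan. The benefit is subject safety; the times differ too much between settings for comparisons across sessions.
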